With funding from a Career Development Award from the Veteran's Affairs (VA) and rigorous formative research, we developed a technology-assisted weight management intervention, called Goals for Eating and Moving (GEM). This intervention is based on the 5As framework (assess, advise, agree, assist, arrange) as recommended by the United States Preventive Services Task Force and reimbursed by the Centers for Medicare and Medicaid Services. The GEM intervention uses a tablet-delivered online tool to facilitate in-person and telephone-delivered health coaching by non-clinical staff, provide tailored patient education materials, and activate patients to set behavior change goals and discuss weight management treatments with their healthcare teams. Preliminary data suggests that the GEM intervention is feasible and acceptable to Veterans and VA staff and facilitates 5As counseling. An ongoing RCT will determine if it promotes weight loss.

The Patient-Centered Medical Home model is an expanded care model emphasizing patient-centered care delivered by inter-professional teams of individuals working to integrate evidence based approaches to improve individual and population health.^{14,15} However, it is unclear how the Patient-Centered Medical Home model can be used to address barriers to 5As implementation, improve weight management counseling, and increase participation in intensive weight management programs. We developed GEM (Goals for Eating and Moving), an innovative, technology-assisted 5As-based intervention for Medical Homes to promote weight loss, behavior change, and participation in intensive weight management programs. To establish the efficacy of the GEM intervention, we will conduct a cluster randomized controlled 12-month intervention of 16 primary care teams at two urban healthcare systems with Medical Home models of care to compare the GEM intervention (intervention arm) with Enhanced Usual Care (educational materials; control arm).

Specific Aims

1. Test the impact of the GEM intervention on weight change, and clinical and behavioral outcomes.
2. Identify predictors of weight loss in the GEM intervention arm related to: a) goal-setting processes and b) intervention components
3. Determine the impact of the GEM intervention on obesity-related counseling practices and attitudes in primary care providers.

Hypothesis

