- Participated in MOVE!, DPP, or another intensive weight management program (>4 sessions) in the past year,
- Have a history of bariatric surgery,
- Are pregnant, breastfeeding or become pregnant during the intervention period,
- Have a provider who states they should not participate,
- Have self-reported inability to read at 5th grade level.
- Currently take weight-loss medications or diabetes medication that may impact weight change
- Receive chemotherapy or cancer treatment
- Had metastatic cancer in the last 6 months
- Does not want to lose weight

We are excluding individuals with any of the above listed conditions as this will likely impact their ability to fully participate in this study. Additionally, some of these listed health conditions may limit physical activity. As this intervention includes telephone weight management counseling and reviewing of printed weight management materials, we are excluding participants without a telephone or participants who cannot read material written at the 5th grade level or above.

We will use phone screen and EHR information to verify inclusion and exclusion criteria.

Vulnerable Subjects

No vulnerable populations will be included as part of this weight management intervention study.

III. Methods and Procedures

[figure not shown]
We will conduct a cluster-randomized controlled trial of the GEM intervention at two healthcare systems in New York City: The VA New York Harbor Healthcare System (Manhattan campus) and Montefiore Medical Group (4 sites affiliated with New York City Research and Improvement Networking (NYC RING) practice-based research network. Participants will be randomized at the team level (19 teams with approximately 28 providers and 512 patients to achieve a sample size of 384 patients at 12 month follow-up for the primary outcome assessment). The primary care teams will be randomized using a random number generator (block randomization with block size of four) to either the GEM Intervention or Enhanced Usual Care arms. Randomization will be stratified by healthcare system (MMG and VA).

Intervention Arm – GEM

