Impact of the GEM intervention on weight change, and clinical and behavioral outcomes:

The primary outcome is mean weight loss at 12 months. Mann-Whitney tests for continuous outcomes (e.g., weight loss) and Fisher's exact tests for categorical outcomes (e.g., whether or not patients achieve $\geq 5\%$ weight loss) will be used to compare the two intervention arms at 12 months. Unadjusted confidence intervals will be computed to compare the effects of the GEM intervention on outcomes with the effects of enhanced usual care on outcomes. Moreover, we will use repeated measures modeling, based on mixed models, to compare outcome variables between intervention arms, using all the data at baseline and three follow-up visits. Such modeling can adjust for baseline characteristics (e.g. diabetes, gender), taking into account: a) the correlation among patients within providers, and b) the correlation among repeated measures within patients. Model-based adjusted confidence intervals will be provided to also measure the effects of the intervention on outcomes. Although the repeated measures modeling can address missing data automatically, assuming it is missing at random, we will further use a multiple imputation procedure to conduct sensitivity analyses under the assumption of missing data not at random. The sensitivity analyses will use pattern-mixture models to examine if the statistical findings are robust across several scenarios, including the least-favorable scenario where the missing data from the GEM intervention arm follows the same pattern as that of the observed data from the usual care arm.

Predictors of weight loss in the GEM intervention arm related to: a) goal setting processes and b) intervention components: We will use visualization tools, such as scatterplots and descriptive analyses (e.g., Spearman correlation coefficients) to display the association between weight change and potential predictors. Multivariate regression models will be used to examine the effects of those predictors, which we suspect will be associated with weight loss in the intervention arm. Multivariate linear regression models will be considered for continuous outcomes and multiple logistic regression models will be considered for binary outcomes. Missing data will be dealt with using inverse-probability-weighted methods.

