 - Health Coaches: Health coaching patients and data collection

VI. Subject Identification, Recruitment, and Consent/Assent

Method of Subject Identification and Recruitment

- ❖ **Primary Care Teams** – Primary care teams at each site that meet the eligibility criteria below will be separately assigned a number using a random number generator, and the first seven teams selected at each site will enroll in the study for a total of 19 primary care teams (11 VA and 8 MMG). Individual providers will be allowed to opt out of the study. We do not anticipate that providers will drop out once enrolled, based on the VA PROVE study where all 18 eligible teams and 51/52 providers participated for the duration of the study.⁶⁵ While pods (at MMG) and PACTs (at VA) have variable numbers of providers and patients, we will recruit 2-3 providers from each team prior to randomization to ensure similar numbers of teams, providers, and patients in each arm. **Table 2** (below) provides an overview of the staffing/patient population for each site.

[figure not shown]
Table 2: Description of PC staffing and patient populations at each of the VA and MMG sites (Data from the VA PC Almanac as of May 2015 or from MMG site director budget reports)

Site	#Teams (Pods or PACTs)	# Providers	Total # Patient s in PC	% Obese	% Female	% Hispanic or Latino
VA Brooklyn	12	24	13,219	32.7	11%	21%
VA Manhattan	11	28	13,813	26.7	8%	
MMG Bronx East	3	17	24,917	47.0	62%	38%
MMG Grand Concourse	2	11	17,841	41.0	67%	40%
MMG University Avenue	2	9	3,679	42.0	58%	79%
MMG Castle Hill	1	7	6,079	45.6	59%	58%

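### No analysis of 12-month weight loss is named as deciding, and the first one listed ignores randomisation by team

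*Combined protocol and SAP*

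**What the plan says.** Section III (Methods and Procedures) sets the unit of allocation: "Participants will be randomized at the team level". It gives 19 teams, about 28 providers and 512 patients, with 384 patients expected at 12 months and stratification by healthcare system. The introduction instead describes a "cluster randomized controlled 12-month intervention of 16 primary care teams".

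The Data Analysis paragraph on the impact of GEM on weight change states: "The primary outcome is mean weight loss at 12 months". The next sentence compares the arms at 12 months using "Mann-Whitney tests for continuous outcomes (e.g., weight loss") and Fisher's exact tests for categorical outcomes such as 5% weight loss. Then: "Unadjusted confidence intervals will be computed to compare the effects of the GEM intervention on outcomes". No cluster term is mentioned for any of these. Provider-level outcomes have their own paragraph, so these tests are on patients.

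The paragraph continues: "Moreover, we will use repeated measures modeling, based on mixed models, to compare outcome variables between intervention arms". This model uses baseline and three follow-up visits and accounts for repeated measures and for "the correlation among patients within providers". Team is not mentioned.

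**The concern.** Patients in one team share an allocation, staff and a setting, so their outcomes may be correlated. A patient-level Mann-Whitney test and an unadjusted interval treat about 384 completers as independent, although only 16 to 19 units were randomised. Chance differences between teams can then be read as a GEM effect. The Mann-Whitney test also does not estimate the quantity named as primary, a difference in means.

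The mixed model is better suited, but the plan does not say that it decides, which of its contrasts is the primary one, or that it accounts for team. If the two analyses disagree, nothing in the plan says which is the trial's answer.

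**Working it through.** **The plan's own figure.** Under Number of Subjects, 75% retention and 384 completers require 384 / 0.75 = 512 enrolled, as stated. The documents give no significance level, power, effect size, SD or ICC, so the 384 cannot be reproduced and no design effect can be read from it.

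**Inputs.** From the documents: 384 patients at 12 months; 19 teams (or 16); about 28 providers. Assumed: two-sided 5% level; ICC 0.01, 0.02 or 0.05.

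**Formulas.**
- Patients per team: m = 384/19 = 20.2, or 384/16 = 24.
- Design effect: DE = 1 + (m − 1) × ICC.
- Actual type I error: 2 × (1 − Φ(1.96/√DE)). Coverage is one minus this.
- Shortfall in interval width: 1 − 1/√DE.

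Example, 19 teams and ICC 0.02: DE = 1 + 19.2 × 0.02 = 1.38; √DE = 1.176; 1.96/1.176 = 1.67; error 9.6%; shortfall 15%.

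| Teams | ICC | DE | Type I error | Coverage | Interval too narrow by |
|---|---|---|---|---|---|
| 19 | 0.01 | 1.19 | 7.3% | 92.7% | 8% |
| 19 | 0.02 | 1.38 | 9.6% | 90.4% | 15% |
| 19 | 0.05 | 1.96 | 16.2% | 83.8% | 29% |
| 16 | 0.01 | 1.23 | 7.7% | 92.3% | 10% |
| 16 | 0.02 | 1.46 | 10.5% | 89.5% | 17% |
| 16 | 0.05 | 2.15 | 18.1% | 81.9% | 32% |

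**Check by simulation.** The Mann-Whitney test was simulated with no true effect, a normal outcome, equal-sized teams and 20,000 trials per setting. It rejected in 7.1% / 9.1% / 16.1% of trials with 10 against 9 teams, and in 7.6% / 10.1% / 18.1% with 8 against 8. At ICC 0 it rejected in 4.9%. A separate simulation with blocks of four within strata of 11 and 8 teams (6,000 trials per setting) gave 6.9% / 9.4% / 16.3%.

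**Conflicting answers.** In that second simulation, Mann-Whitney was significant while a t-test on team means was not in 3.1% / 4.8% / 11.0% of null trials, against 1.6% at ICC 0. The team-mean test stayed at about 5%.

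**Clustering by provider only.** A t-test on provider means served as a proxy for a provider random effect, with all correlation placed at team level (20,000 null trials). With 28 providers the error is 5.7% / 7.0% / 8.3%. Section VI says "we will recruit 2-3 providers from each team prior to randomization", which would mean 38 to 57 providers in 19 teams, whereas 28/19 is about 1.5 per team. With 47 providers the error is 6.4% / 8.0% / 11.0%.

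**Few clusters.** With 19 teams, two arms and two strata there are about 19 − 2 − 1 = 16 degrees of freedom. Using 1.96 there gives 6.8% error (7.2% with 16 teams and 13 degrees of freedom), even if team is modelled.

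**Other outcomes.** Fisher's test for 5% weight loss, at an assumed 20% event rate, has error of about 5% / 6–7% / 9–10%. The provider tests of Aim 3 also ignore team, but at ICC 0.05 the error is only 5.3% with 1.5 providers per team and 5.6–6.2% with 2–3.

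**The case against.** The strongest reply is that being listed first does not make a test primary. The plan includes a model for clustered data and builds its missing-data approach on that model, which suggests the model is meant to carry the inference. On that reading the exposure is the provider-only figure, 5.7% / 7.0% / 8.3%, and less if part of the correlation lies with providers: about 5.4% / 5.5% / 6.6% when the ICC is split equally between team and provider. This is a fair reading, but the text does not state it. The model is introduced as an addition, and the Mann-Whitney comparison is the only analysis tied to 12 months.

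The size is also open to challenge. Every ICC is assumed, and at 0.005 the error is only 6.1% with 19 teams. Stratification by healthcare system removes correlation that comes from differences between systems. If half of it did, the Mann-Whitney error would be about 6.2% / 7.1% / 10.5%, against 7.2% / 9.1% / 15.6% in the same simulation with all of it at team level. These points stand. They shrink the inflation in some scenarios but do not remove it.

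The disagreement rates use a team-mean test in place of the planned mixed model, so they only illustrate how often the two could conflict. Unadjusted may simply mean without covariates, but no cluster adjustment is described for those intervals either. The points on Fisher's test and Aim 3 are minor.

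**Conclusion.** The concern holds and should be fixed before analysis. No analysis of the primary outcome is named as deciding, and that finding depends on no assumed number. The first listed test and interval are invalid under team randomisation whenever outcomes correlate within team. At a nominal two-sided 5% level and ICCs of 0.01 to 0.05, all within healthcare system, the error runs from about 7% to 16% with 19 teams and from about 8% to 18% with 16. The mixed model as described reduces the problem but does not remove it, because it names provider and not team.

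**What to change.** - Name one primary analysis: the GEM minus Enhanced Usual Care difference in mean weight change at 12 months, from the planned mixed model. State the significance level.
- Include a random effect for team, a fixed effect for healthcare system, and Kenward-Roger or Satterthwaite degrees of freedom. A provider-within-team effect is optional: with about 1.5 providers per team the two variances will be hard to separate.
- Analyse 5% weight loss with a logistic mixed model or GEE clustered by team, with a small-sample correction.
- Label the Mann-Whitney and Fisher comparisons and the unadjusted intervals as descriptive, and state that they do not decide the primary outcome.
- Reconcile the number of teams (16 or 19) and of providers per team.

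The cost is wording only, since team membership and weights are already collected. Intervals will be wider, as they should be. As a rough guide, √DE × 2.12/1.96 with 19 teams and 16 degrees of freedom gives intervals 18% / 27% / 51% wider than the unadjusted ones at ICC 0.01 / 0.02 / 0.05, and about 8% wider at ICC 0. This scales a simple 12-month comparison; the repeated-measures model with covariates may give a different width.

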Control Arm – Enhanced Usual Care (EUC)

Patients in the EUC arm will receive non-tailored weight management handouts by health coaches (Health Bulletins from the NYC DOHMH).^{79–81} Patients will follow-up with their primary care teams as needed.

Data Collection

Patients: Assessment will occur at the following time points:

- ❖ At Baseline, 6, 12, and 24 months, patients will meet in-person or over the phone (for follow-up) with a research assistant (RA) to complete surveys; measure weight, height, blood pressure, and waist circumference. Baseline surveys will include a pre-survey (completed before receiving GEM Intervention/Enhanced Usual Care). Electronic chart review will also occur at these time points. The RA will administer all surveys and enter the data directly into our REDCap database. To compensate for

travel and time spent completing study measurements, patients will be given \$25 dollars for the baseline study visit, \$30 dollars for the 6-month study visit, \$40 dollars for the 12-month study visit, and \$50 for the follow-up 24-month visit and \$20 dollars for the optional one hour opinion session and 2 follow-up phone calls. During the baseline visit we will encourage patients to sign-up for MyHealtheVet, if they haven't done. In addition, we will inform patients about the VA's secure Annie texting service and help them to sign up, if requested, as another option to receive reminder text messages for appointmentsIf patients are signed-up for MyHealtheVet, they can choose to receive reminders for their upcoming study visits or health coach phone calls electronically via myHealtheVet. Alternatively, patients can choose receive reminder phone calls from secure VA phones lines or via the secure Cisco Jabber application.. Before upcoming phone coaching calls and study visits, we will send reminders via the secure messaging system MyhealtheVet, VA's Annie texting service or make phone calls via secure VA phone lines or via the secure Cisco Jabber application.

- ❖ When performing telephone Coaching Calls (patients in GEM Intervention arm only), Health coaches will use a counseling tool that also facilitates data collection into REDCap database.
- ❖ Chart reviews 12 and 24 months post-baseline visit to explore maintenance of counseling post-intervention

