Primary Care Teams: At 12 months, we will give surveys to providers, which will be administered in paper and then entered into our REDCap database. Alternatively, we will administer the provider survey online via REDCap. Furthermore, we will conduct qualitative interviews, and audiotape select visits.

Future Directions: In future versions of the GEM intervention we would like to add a visualization technique called Mental Contrasting with Implementation Intentions (MCII) that is utilized through an exercise called WOOP (Wish, Outcome, Obstacle, Plan). MCII is a novel, practical strategy that was developed and tested through 20+ years of research to promote motivation and behavior change, particularly for challenging behaviors.¹¹⁰⁻¹¹⁵ In order to obtain data on feasibility and acceptability among Veterans without introducing the burden of an additional visit, we will invite up to 20 participants in either arm at the Manhattan VA site to participate in an optional one hour session at their 24 month visit for an additional \$20. Veterans that agree to this additional session will be reconsented with the revised consent form describing this session. During this session they will receive training on WOOP and will be shown how to use the free downloadable WOOP app.²⁴ We will then ask them to share their opinions on WOOP and the app. We will not collect any information from the WOOP app and discussed this piece of the protocol with the Privacy Officers ([name] and [name]). In addition to this training, we will ask each participant a few brief questions related to goal commitment and stage of change before and after the WOOP training. We will also ask permission to follow up via telephone at 3 days and 1 month after the training to see if they have used the technique to make any changes related to weight, diet or physical activity. The materials for this session can be found in Appendix F.

Data Analysis and Data Monitoring

First, all the variables will be summarized (intention-to-treat approach) using mean (with standard deviation) and median (with interquartile range for continuous variables and frequency table for categorical variables) overall and by interventions arms, respectively. Then, Mann-Whitney tests for continuous variables and Fisher's exact tests for categorical variables will be used to check if both providers' and patients' baseline characteristics are balanced between the interventions arms.

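### No between-arm analysis is specified to use the patient's own baseline value of the outcome, and the mixed model leaves its baseline handling and its 12-month contrast unstated

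*Combined protocol and SAP*

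**What the plan says.** The relevant text is in the Combined protocol and SAP, section III, Data Analysis and Data Monitoring, in the paragraph on the impact of GEM on weight change and on clinical and behavioral outcomes. It begins: "The primary outcome is mean weight loss at 12 months". Two routes to the between-arm comparison follow, and the text does not say which one leads.

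- **Simple tests at 12 months.** These are "Mann-Whitney tests for continuous outcomes (e.g., weight loss) and Fisher's exact tests for categorical outcomes". Neither test takes a covariate. The accompanying intervals are described in these words: "Unadjusted confidence intervals will be computed to compare the effects of the GEM intervention on outcomes".
- **A mixed model**, planned "to compare outcome variables between intervention arms, using all the data at baseline and three follow-up visits". On covariates it says "Such modeling can adjust for baseline characteristics (e.g. diabetes, gender", which is permissive and gives examples only. The model is to allow for correlation within providers and for "the correlation among repeated measures within patients".

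The paragraph does not mention an arm-by-visit term, a constraint on the baseline means, or the contrast that will be reported for 12 months. Just before it, Mann-Whitney and Fisher tests "will be used to check if both providers' and patients' baseline characteristics are balanced between the interventions arms", but no adjustment follows from the result.

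Under Data Collection, research assistants "measure weight, height, blood pressure, and waist circumference" at baseline and at each follow-up, and surveys are completed at the same visits. The baseline values will therefore be in hand.

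**The concern.** A patient's own baseline value is usually the strongest single predictor of the 12-month value. The plan collects it but does not commit to using it as a predictor. The mixed-model text fits at least three different 12-month contrasts: raw 12-month values by arm, changes from baseline with free baseline means, or a contrast with baseline means held equal. They differ in precision and in how far a chance baseline difference between arms moves the estimate. With only 19 randomized teams, such differences are to be expected. Leaving the form open also allows the choice to be made after the data are seen.

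One of the two example covariates, diabetes, is also an exclusion criterion in section II. Those two places need reconciling. As they stand, that covariate can explain little.

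**Working it through.** **Inputs from the documents.** 512 enrolled, 384 completing, 75% retention and 20% participation (section II, Number of Subjects); 19 teams (section III); visits at baseline, 6, 12 and 24 months (Data Collection). The plan's own arithmetic reproduces: 384 / 0.75 = 512. Also 512 / 0.20 = 2,560 against the stated 2,615, about 2% apart. The documents give no power, effect size, SD, intracluster correlation (ICC) or baseline-to-12-month correlation (rho). Rho and the ICC are therefore assumptions, shown as ranges.

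**Two visits, complete data, no clustering.** In units of the outcome variance, the contrast is proportional to 2(1 - rho) for change scores, 1 for raw 12-month values and 1 - rho² with baseline adjustment. Adjusted over change is (1 - rho²) / [2(1 - rho)] = (1 + rho)/2. Adjusted over raw is 1 - rho².

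| Assumed rho | Adjusted / change | Reduction | Adjusted / raw | Reduction |
|---|---|---|---|---|
| 0.4 | 0.70 | 30% | 0.84 | 16% |
| 0.5 | 0.75 | 25% | 0.75 | 25% |
| 0.6 | 0.80 | 20% | 0.64 | 36% |
| 0.90 | 0.95 | 5% | 0.19 | 81% |
| 0.95 | 0.975 | 2.5% | 0.0975 | 90% |
| 0.97 | 0.985 | 1.5% | 0.059 | 94% |

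At rho 0.5, the 384 completers analyzed by change scores are worth 384 × 0.75 = 288 under adjustment. Where adjustment would give 80% power, change scores give 67.9%. At rho 0.95 they give 79.0%.

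**Four visits, clustering and dropout.** Generalized least-squares variances were computed for 18 teams of 28 patients (504, close to the plan's 512). The team effect was constant over time with ICC 0.02, rho was the same between all visits, and 25% of patients were missing from 12 months on. The free-baseline change contrast was compared with the model that holds arm means equal at baseline.

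- At rho 0.4, 0.5 and 0.6 the variance ratios are 1.19, 1.15 and 1.12. The reductions are 1 - 1/1.19 = 16%, 1 - 1/1.15 = 13% and 1 - 1/1.12 = 11%.
- At rho 0.90 and 0.95 the ratios are 1.03 and 1.01.
- For raw 12-month values against the constrained model, the ratio is 1.66 at rho 0.5 (reduction 1 - 1/1.66 = 40%) and 2.46 at rho 0.7.

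With ICC 0 and no missing data, the constrained model has the same variance as baseline adjustment, 1 - rho².

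**Chance imbalance.** The mean team size is 512 / 19 = 26.9. At ICC 0.02 the design effect is 1 + 25.9 × 0.02 = 1.52. The standard error of the baseline difference is √(4 × 1.52 / 512) = 0.109 SD, so a difference of 0.1 SD is ordinary. It shifts a change contrast by -(1 - rho) × 0.1 SD, which is -0.05 SD at rho 0.5 and -0.005 SD at rho 0.95. It shifts a raw 12-month contrast by rho × 0.1 SD, which is +0.05 and +0.095 SD.

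**The case against.** Much of the case on the other side stands, and it limits the point in five ways.

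- A reader might infer that having baseline among the responses is itself the fault. It is not. With arm means constrained equal at baseline, a four-visit model is as efficient as covariate adjustment, and the text does not rule that form out. What is missing is the specification.
- A reader might infer that the plan rules out baseline adjustment. It does not. The model may adjust for baseline characteristics, and the two named are only examples. The supportable statement is that no analysis is specified to adjust for the baseline value.
- A reader might carry the 90% figure at rho 0.95 over to the primary outcome. The plan does not propose comparing raw 12-month weights. Weight loss already subtracts each patient's baseline weight, so the relevant gain is the few percent over change scores.
- A reader might argue that weight loss is zero for everyone at baseline, so that the model is ill-formed. The natural reading is that measured weight is modeled at each visit, and nothing in the text contradicts that.
- The two-visit formula overstates the gain over change scores in this design. Clustering and dropout reduce it to roughly half, on the assumptions shown.

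What remains is that the Mann-Whitney and Fisher comparisons cannot use the baseline value as a predictor, that the mixed model does not commit to a form, and that the plan does not say whether secondary outcomes are compared as values or as changes.

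**Conclusion.** The point holds as a gap in specification that should be closed. If arm means are left free at baseline, precision is lost and chance imbalance enters the 12-month contrasts.

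For the primary outcome the effect is minor: about 1.5-5% of variance at assumed rho 0.90-0.97, or 1-2 points of power at rho 0.90-0.95. It should not be presented as a threat to that result.

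For blood pressure, diet and activity at assumed rho 0.4-0.6, adjustment would cut variance by 20-30% against change scores in the simple case, by roughly 11-16% with ICC 0.02 and 25% missing data, and by 16-36% or more against raw 12-month values.

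These sizes rest on assumed correlations and an assumed ICC. The documents supply neither. The gap itself can be read directly from the text and does not depend on them.

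**What to change.** Name the mixed model as the main between-arm analysis for continuous outcomes, and name the 12-month arm contrast as the reported effect. Then choose one of two forms:

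- model the 6-, 12- and 24-month values as responses, with the baseline value of the same outcome as a covariate; or
- keep all four visits as responses with arm means constrained equal at baseline. This form also keeps patients who have no follow-up visit.

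Do not enter baseline both as a response and as a covariate. For the primary outcome, model body weight in this way. Keep the unadjusted Mann-Whitney tests as supportive only, since they cannot take a covariate. Reconcile the use of diabetes as an example covariate with its place among the exclusions.

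The cost is a few sentences of analysis text and a change in which analysis leads. No new data, visits or patients are needed. The change should be made before outcome data are examined by arm.

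### Healthcare system, the randomisation stratum, is in no pre-specified between-arm analysis, and the mixed model clusters by provider instead of the randomised team; specify system and team-level clustering of change together

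*Combined protocol and SAP*

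**What the plan says.** **Design.** Section III states "Participants will be randomized at the team level (19 teams with approximately 28 providers and 512 patients", in blocks of four, and "Randomization will be stratified by healthcare system (MMG and VA". Section VI (Primary Care Teams) gives the strata as "for a total of 19 primary care teams (11 VA and 8 MMG".

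**Analysis.** Under Data Analysis and Data Monitoring, the 12-month comparison uses Mann-Whitney and Fisher's exact tests with unadjusted intervals. A repeated-measures mixed model follows, "using all the data at baseline and three follow-up visits". It accounts for "the correlation among patients within providers" and for repeated measures within patients. On covariates the text is "Such modeling can adjust for baseline characteristics (e.g. diabetes, gender". It adds: "Model-based adjusted confidence intervals will be provided". Provider-level outcomes are compared with the same two unstratified tests. System, site and stratum appear in none of these analyses.

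**Eligibility.** The Exclusion Criteria list diabetes among the excluded conditions. A separate item excludes only diabetes medication that could affect weight.

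**The concern.** Teams are allocated within system, so system is the obvious covariate to fix in advance. The plan leaves it to choice after the data are seen. Of the two covariates it does name, diabetes is constant if the exclusion is applied as written, and gender is only a partial stand-in for system.

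The random-effects structure decides whether adding system helps. Team is the randomised unit, but only providers and patients are modelled. At stake are the calibration of the model-based intervals and, once the clustering is right, the power of a comparison that rests on 19 clusters.

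**Working it through.** **1. The plan's own arithmetic.** 384/0.75 = 512 enrolled, as stated. 512/0.20 = 2,560 to approach, against 2,615 stated (2.1% higher). The 384 cannot be derived, because no alpha, power, effect, SD or ICC is given.

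**2. Inputs.** From the documents: 19 teams (11 VA, 8 MMG), blocks of four within system, 384 completers, so 384/19 = 20.2 per team. Counts conflict elsewhere: the introduction has 16 teams, and "we will recruit 2-3 providers from each team prior to randomization" implies 38 to 57 providers against about 28. Assumed: two-sided 5%; 1:1 allocation; equal teams of 20; all ICC at team level, 0.02 or 0.05, for 12-month weight change; effect 0.4 SD; system difference d from 0 to 0.35 SD.

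**3. The model with intercepts constant over visits.** Baseline is one of the repeated measures, so anything constant over visits cancels out of the change. In simulated datasets with baseline and one follow-up visit, the arm-by-visit estimate and SE equalled patient-level least squares on change. They did not move when a system main effect was added (for example 0.0941, SE 0.1177, both times, with provider and patient intercepts).

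The resulting error follows from the design effect 1 + (20 − 1) × ICC:
- ICC 0.02: 1.38. Effective critical value 1.96/√1.38 = 1.67, so type I error is 9.5% (simulated: 9.4%).
- ICC 0.05: 1.95. 1.96/√1.95 = 1.40, so type I error is 16.0% (simulated: 16%).

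System-by-visit does reach the change, but without team clustering it does not repair calibration. At d = 0.35, type I error goes from 9.9% to 10.3% (ICC 0.02) and from 15.8% to 16.1% (ICC 0.05).

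**4. A team-level model of change, without and with system.** The variance of a team mean is ICC + (1 − ICC)/20 = 0.02 + 0.049 = 0.069, so the true SE of the arm contrast is √(4 × 0.069/19) = 0.121. Stratified allocation keeps system out of that SE. A model without system still counts it as between-team variance: d² × (11/19) × (8/19) = 0.030 at d = 0.35. The reported SE becomes √(4 × 0.099/19) = 0.144 (simulated: 0.145), about 20% too large. Simulation, 10,000 trials per setting, effect 0.4 SD:

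| ICC 0.02, equal teams | d = 0 | 0.15 | 0.25 | 0.35 |
|---|---|---|---|---|
| Type I error without system | 4.2% | 3.9% | 3.0% | 2.0% |
| Power without system | 87.6% | 85.5% | 81.5% | 75.7% |

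With system, type I error is 4.1% and power 87.3%. The loss from omitting it is therefore about 0, 2, 6 and 11 to 12 points. A separate simulation at d = 0.35 gave 77% without and 88% with, a gap of 11.

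At ICC 0.05, power without system is 74.1, 72.1, 68.6 and 63.5%, against 74.0% with it.

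**5. Gender as a proxy.** Table 2 gives 63.1% women at MMG (patient-weighted). With 8% at the VA and the 52% expected overall, the VA share is (63.1 − 52)/(63.1 − 8) = 0.20, and the gender-system correlation (phi) is 0.44. With gender already in the team-level model (ICC 0.02, equal teams), the gain from adding system at d = 0.15, 0.25 and 0.35 is:
- 0.8, 2.8 and 6.5 points if none of the difference is due to gender;
- 0, 0.5 and 1.1 points if half is;
- a loss of 0.4 to 0.5 points if all is.

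**The case against.** **What stands.** The covariate wording is open, so system is not ruled out. Stratification already balances it, and leaving it out does not bias the comparison towards GEM. The larger defect is the missing team level. The power gain from system appears only once that is corrected, and the true SE hardly changes (0.121 without, 0.120 with). The size rests on an undocumented system difference: the 11-point figure needs 0.35 SD, nearly the assumed treatment effect. The documents give reasons to expect some difference (the VA's MOVE! programme and the gender mix) but no figure. The MOVE! reason is weakened because recent users of either intensive programme are excluded and coaches may steer patients to either.

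**Two stronger readings that the documents do not support.**

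A reader might infer that the plan's model-based intervals are too wide because system is omitted. That holds for a team-level model, which the plan does not contain. With constant provider and patient intercepts, the planned intervals are too narrow.

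A reader might also infer that adding system alone to the planned model raises type I error. This happens in a single-outcome, change-score or provider-by-visit model. There, at 0.35 SD with two providers per team, it rises from 4.6% to 6.4% (ICC 0.02) and from 6.6% to 9.1% (ICC 0.05), because system variance had been masking the team correlation. The plan specifies none of these forms. With constant intercepts a system main effect changes nothing, and system-by-visit moves the error by about 0.3 to 0.4 points.

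**Conclusion.** The point holds as a matter of pre-specification and calibration, and is one to consider. The randomisation stratum is named in no between-arm analysis, and the modelled cluster is not the randomised unit.

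If the intercepts are constant over visits, type I error is about 9% (ICC 0.02) to 16% (ICC 0.05) with equal teams, and a system main effect does not help. Once team-level clustering of change is in place, omitting system costs about 0, 2 and 11 power points at differences of 0, 0.15 and 0.35 SD (ICC 0.02, effect 0.4 SD), and less where gender explains part of the difference. The ICC, the effect and the system difference are all assumptions. The model check used baseline and one follow-up visit only.

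The diabetes example is a small inconsistency of wording.

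**What to change.** In the mixed model for between-arm comparisons, pre-specify:

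1. healthcare system (VA or MMG) and system-by-visit as fixed effects;
2. a team-level random effect that acts on change, either team-by-visit or a team intercept in a model of change from baseline;
3. small-sample degrees of freedom for the arm contrast.

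The visit interactions are needed because a system main effect and a constant team intercept both cancel out of the change. Items 1 and 2 belong together.

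Fix the covariate list in advance, and reconcile the diabetes example with the two exclusion items. Stratified versions of the Mann-Whitney and Fisher tests are optional, for consistency only; they would not correct for clustering.

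**Cost:** a few lines in the SAP and no new data. System takes one between-team degree of freedom (16 instead of 17), about 0.3 to 0.5 power points if the systems do not differ.
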